16.5 Neurologic Exam

A neurologic exam will be performed at screening, on Day 1 (before the first injection of study drug), and at Weeks 13 and 52. A neurologic exam will also be performed as needed at the Investigator's discretion throughout the study and, if applicable, at discontinuation from the study. The neurologic exam will consist of 9 sections to evaluate: 1) level of consciousness; 2) speech; 3) cranial nerves; 4) motor; 5) sensory; 6) coordination; 7) gait; 8) reflexes; and 9) Romberg test (Appendix H).

16.6 Dental Exam

An oral dental exam (Appendix I) will be performed by a licensed dentist (DDS or DMD) at screening and Weeks 4, 13, 26, and 52 or, if applicable, at discontinuation from the study. Four bite-wing radiographs or panoramic imaging will be obtained at screening and Weeks 26 and 52 or at discontinuation from the study.

A dental exam will also be performed as clinically warranted based on predefined safety criteria (e.g., persistent dry mouth). See Section 16.2.3 for findings to be reported as dental adverse events. Subjects will be advised to continue their dental care visits with their regular dentist throughout the course of the study.

Subjects or their caregiver will also complete a dental questionnaire at screening (Appendix I).

16.7 Oral Exam

An oral exam (Appendix I) will be performed by the Investigator at each study visit where a dental exam is not required. This will include a visual inspection for detection of any major dental issues and, if clinically warranted, the subject will undergo a dental exam (see Section 16.6). See Section 16.2.3 for findings to be reported as dental adverse events.

16.8 Physical Exam

A complete physical exam will be performed at screening and Weeks 4, 13, 26, 39, and 52, or, if applicable, at discontinuation from the study. The complete exam will involve gross examination of general appearance; head, ears, eyes, nose and throat; skin; extremities; chest; abdomen; and lymph nodes. Cardiac and pulmonary auscultation and measurement of vital signs (see Section 16.3) and weight will also be conducted as part of the complete physical exam.

A brief physical exam, consisting of cardiac and pulmonary auscultation and measurement of vital signs (see Section 16.3) will be performed on Day 1 (before the first injection of study drug) and at Weeks 8, 17, 30, and 43. Height will be recorded at screening only.

FVC will be measured in all subjects with ALS, and in other subjects if warranted, at the discretion of the Investigator at screening, before the first injection of study drug on Day 1, at Weeks 4, 8 (as clinically warranted), and 13. Thereafter, FVC will be checked if warranted at Investigators' discretion (such as if the subject has ALS).

16.9 Columbia Suicide Severity Rating Scale (C-SSRS)

The C-SSRS measures both suicidal ideation and suicidal behavior and will be completed on Day 1 (before the first injection of study drug), at each subsequent study visit, or, if applicable, at discontinuation from the study. The Baseline version of the C-SSRS (Appendix J) will be used to assess lifetime suicidality on Day 1. At all other protocol-specified time points, the C-SSRS – Since Last Visit version (Appendix K) will be used to assess the subject's suicidality since the last assessment.

The C-SSRS has three subscales: suicidal ideation, suicidal behavior, and intensity of suicidal ideation. Both suicidal ideation subscale and suicidal behavior subscale have 5 yes-no items each, with a sum score ranging from 0 to 5 and higher score indicating greater severity. The intensity of suicidal ideation has 5 items, with a sum score ranging from 2 to 25 and higher score indicating greater risk.

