17.6 Safety Endpoints

Safety endpoints include adverse events and AESI, vital signs and weight, neurological exam, physical examination, dental exam, C-SSRS, and clinical laboratory tests. Adverse events will be coded using the Medical Dictionary for Regulatory Activities (MedDRA) adverse event dictionary.

For safety endpoints, records with valid data within each visit or assessment time point will be identified for initial and repeat, where applicable. The initial record will be used in statistical analysis, whereas all records will be presented in data listings. Missing or invalid data will be treated as missing for the corresponding visit or time point.

The baseline of each treatment session consists of the corresponding measurement value obtained at pre-injection of each treatment session (i.e., Day 1, Weeks 13, 26, and 39).

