Each of the three C-SSRS subscales (suicidal ideation, suicidal behavior, and intensity of suicidal ideation) will be summarized descriptively for continuous variable at each pre-injection visit (i.e., Day 1, Weeks 13, 26, and 39) and at each post-injection time point of 4 weeks post-injection (i.e., Weeks 4, 17, 30, and 43), 8 weeks post-injection (i.e., Week 8, first Treatment Session only), and 13 weeks post-injection (i.e., Weeks 13, 26, 39, and 52).

The change scores in C-SSRS subscales from pre-injection at 4 weeks, 8 weeks (first Treatment Session only), and 13 weeks post-injection will be analyzed, using a paired t-test where applicable, by treatment dose group defined in Section 17.3 for the safety population (i.e., low dose, medium dose, and high dose).

Clinical laboratory tests of hematology, chemistry, and urinalysis (specific gravity and pH) will be summarized descriptively at available visits. Qualitative analysis of laboratory tests in terms of abnormality will be performed, using the shift-table method, for individual post-screening visits. Abnormal findings of clinical laboratory tests for individual subjects will be provided by data listing.

Abnormal findings of dental exam for individual subjects will be provided by data listing.

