2.6.2 Safety measures

Adverse events are recorded at each study visit, starting from the first injection of MYOBLOC on Day 1 of Treatment Session 1 and ending at study completion (i.e., 52 ± 1 week). Subjects who discontinue because of an adverse event before study completion will be contacted 13 weeks (±3 days) after their last injection of study drug to assess the adverse event. Serious adverse events, adverse events of special interest, and other immediately reportable adverse events were collected during the study period (or within 13 weeks ±3 days of last study drug injection for subjects discontinuing participation prematurely). Dental and oral health are followed closely throughout the course of the study by monitoring dental adverse events (DAE), as defined in the study protocol.

Vital signs (blood pressure, pulse, respiratory rate, and temperature) are measured after sitting quietly for at least 5 minutes at screening and each study visit, if applicable, at early termination from the study.

Subjects' suicidal ideation and behavior are measured at each study visit (including Day 1 and Weeks 4, 8, 13, 17, 26, 30, 39, 43, and 52) or, if applicable, early termination from the study, using the Columbia Suicidal Severity Rating Scale (C-SSRS). The C-SSRS baseline version (Appendix I of the protocol) will be used for Day 1, whereas the C-SSRS since last visit version (Appendix J of the protocol) will be used for all of the other visits. The C-SSRS has three subscales: suicidal ideation (Categories 1-5), suicidal behavior (Categories 6-10), and intensity of suicidal ideation. Both suicidal ideation subscale and suicidal behavior subscale have 5 yes-no categories each, with a sum score ranging from 0 to 5 and higher score indicating greater severity.

Category 1 – Wish to be Dead

Category 2 – Non-specific Active Suicidal Thoughts

Category 3 – Active Suicidal Ideation with Any Methods (Not Plan) without Intent to Act

Category 4 – Active Suicidal Ideation with Some Intent to Act, without Specific Plan

Category 5 – Active Suicidal Ideation with Specific Plan and Intent

- Category 6 – Actual Attempt
- Category 7 – Interrupted Attempt
- Category 8 – Aborted Attempt
- Category 9 – Preparatory Acts or Behavior
- Category 10 – Suicidal Behavior

The intensity of suicidal ideation has 5 items (2 are scored from 1 through 5 and the other three from 0 to 5), with a sum score ranging from 2 to 25 where higher score indicate greater risk.

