2.9.2 Safety analysis

Safety measures include adverse events, adverse events of special interest (AESI), dental adverse events (DAE), adverse events associated with distant spread of toxin effect, vital signs and weight, physical exam, neurological exam, dental exam, oral exam, and clinical laboratory tests, as well as lung functioning test for ALS subjects. Adverse events will be coded using the Medical Dictionary for Regulatory Activities (MedDRA) adverse event dictionary.

Like for effectiveness analyses, the baseline for safety analysis includes the pre-injection visits of Day 1, and Weeks 13, 26, and 39, respectively, for each of the treatment sessions 1 through 4.

Drug Exposure

Frequency of drug exposure will be calculated based on the number of injections of study drug administered. Duration of drug exposure will be calculated for each subject for the average duration of individual treatment sessions and total duration of treatment sessions, with the former being the average of the durations of individual treatment sessions the subject has received and the latter being the sum of the durations of individual treatment sessions the subject has received. Duration of drug exposure will be summarized for the safety population as defined in Section 3.1.

Early Termination

Subjects' study disposition will be summarized. A listing will be provided for all early terminations. This listing will include a subject's demographic variables, primary diagnosis, number of injections administered, and the primary reason for early termination.

Adverse Events, AESI, and DAE

All of adverse events will be coded for preferred terminologies using MedDRA. An AE that occurs on the 1st injection date or later will be defined as a TEAE. An AE with start date missing and no valid stop date or stop date being after the first injection date will be considered as a TEAE. TEAEs will be further separated by treatment session.

TEAEs, AESIs, DAEs, and adverse events associated with distant spread of toxin effect will be analyzed by session. Frequency of these types of adverse events will be calculated for each body system (or system organ class, SOC), by preferred term, for number of subjects and proportion reporting the event. The severity of adverse events and the relationship to study medication will be summarized for each body system and preferred term.

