Withdrawals due to adverse events will be summarized for each body system and preferred term. Serious adverse events (SAEs) (including deaths) will be listed for individual events.

Narratives will be provided for all deaths, non-fatal serious adverse events, and subjects withdrawn due to adverse events.

Vital Signs and Weight

Vital signs and weight will be summarized descriptively by treatment session at pre-injection (i.e., Day 1 and Weeks 13, 26, and 39) and at each post-injection time point of 4 weeks post-injection (i.e., Weeks 4, 17, 30, and 43), 8 weeks post-injection (i.e., Week 8 first treatment session only), and 13 weeks post-injection (i.e., Weeks 13, 26, 39, and 52). The change scores in vital signs and weight from baseline at 4 weeks, 8 weeks (first treatment session only), and 13 weeks post-injection will be summarized descriptively.

Neurologic Exam

Abnormal findings of neurological exam data will be listed, respectively, for individual subjects.

Lung Functioning Test

Findings of forced vital capacity (FVC) data will be listed, respectively, for individual subjects.

Physical Examination

A complete Physical Examination was performed at Screening, Week 4, Week 13, Week 26, Week 39, Week 52, and Early Discontinuation. A brief Physical Examination was performed at Day 1, Week 8, Week 17, Week 30, and Week 43 when body weight, height and body mass index (BMI) were recorded. If any of the Physical Examination findings were abnormal and clinically significant prior to treatment, the event was recorded as medical history, while if occurred after treatment the event was recorded as a TEAE.

Suicidality Assessment

For each treatment session, each of the three C-SSRS subscales (suicidal ideation, suicidal behavior, and intensity of suicidal ideation) will be summarized descriptively for continuous variable at each pre-injection visit (i.e., Day 1 and Weeks 13, 26, and 39) and at each post-injection time point of 4 weeks post-injection (i.e., Weeks 4, 17, 30, and 43), 8 weeks post-injection (i.e., Week 8, first treatment session only), and 13 weeks post-injection (i.e., Weeks 13, 26, 39, and 52). The change scores in C-SSRS subscales from pre-injection at 4 weeks, 8 weeks (first treatment session only), and 13 weeks post-injection will be summarized descriptively.

Dental Examination and Oral Examination

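### Session 1 C-SSRS change subtracts a lifetime Day 1 score from a since-last-visit score, so its mean leans toward apparent improvement

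*Protocol*

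**What the plan says.** Protocol 16.9 sets two recall windows. For the first: "The Baseline version of the C-SSRS (Appendix J) will be used to assess lifetime suicidality on Day 1". At all other time points the Since Last Visit version assesses "suicidality since the last assessment". SAP 2.6.2 agrees on the forms: "The C-SSRS baseline version (Appendix I of the protocol) will be used for Day 1", with the Since Last Visit version at all other visits. (The appendix letters differ between the two documents; this has no bearing here.)

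Both documents make Day 1 the Session 1 baseline. Protocol 17.6: "The baseline of each treatment session consists of the corresponding measurement value obtained at pre-injection of each treatment session". SAP 2.9.2: "the baseline for safety analysis includes the pre-injection visits of Day 1, and Weeks 13, 26, and 39".

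Both then plan change from that baseline for the three subscales. In Protocol 17.7 the changes at 4, 8 and "13 weeks post-injection will be analyzed, using a paired t-test where applicable, by treatment dose group". SAP 2.9.2 plans descriptive summaries of "The change scores in C-SSRS subscales from pre-injection at 4 weeks, 8 weeks (first treatment session only), and 13 weeks post-injection", and says the subscales themselves "will be summarized descriptively for continuous variable at each pre-injection visit" and at each post-injection time point. SAP 5.12 announces inferential statistics for the C-SSRS but ends by calling the change summaries descriptive. SAP 2.9 includes the mean among the standard descriptive statistics.

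No section in the supplied text names a recent-recall Day 1 score, exempts Day 1 from the change, or warns about the differing windows.

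**The concern.** A change score has meaning only if both values measure the same thing. Here the first covers a lifetime and the second covers four or five weeks. A subject whose ideation lies wholly in the past scores above zero on Day 1 and zero afterwards, and so counts as improved. A subject with both past and new ideation can also score zero or below: two lifetime ideation items endorsed and one newly endorsed give a change of 1 - 2 = -1, although ideation occurred after injection.

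The C-SSRS is one of four safety endpoints listed in Protocol 9.1, and long-term safety is the primary objective. In a single-arm study, a flat or falling Session 1 mean could be read as reassurance when it reflects only the longer look-back on Day 1.

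**Working it through.** **No plan figure to reproduce.** The documents state no expected C-SSRS change and no prevalence of lifetime or recent ideation. SAP 2.5 says no sample size estimation was performed. The value n = 187 below comes from SAP 2.5; every prevalence, score and risk ratio is an assumption.

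**Direction.** A lifetime window contains any recent window. For the ideation and behavior sums (0 to 5, higher is worse), and for intensity as SAP 2.6.2 redefines it (maximum ideation category, 0 if none), each subject's lifetime Day 1 score is at least as high as a recent-window score would be. Each Session 1 change is therefore at or below its matched-window value, and so is the mean. The shift is zero only if no subject's lifetime history goes beyond the recent window.

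**Worked example.** Mean change = (sum of post-injection scores - sum of Day 1 scores)/n. Four subjects score 2 after injection, and none had current ideation before it.

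- Matched window: (4 × 2 - 0)/187 = 8/187 = +0.043.
- Lifetime Day 1 form, with k subjects scoring 2: (8 - 2k)/187.

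| k (share of 187) | Mean change |
|---|---|
| 4 (2%) | 0.000 |
| 9 (5%) | -10/187 = -0.053 |
| 19 (10%) | -30/187 = -0.160 |
| 37 (20%) | -66/187 = -0.353 |

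The mean does not depend on which subjects overlap; the maximum change does. It is +2 if at least one of the four has no history, and 0 if all four have a lifetime score of 2. The observed post-injection maximum is 2 in both cases.

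**Range.** With 2% post-injection prevalence, lifetime prevalence L and a mean score of 1 to 3 among positives, mean change = (0.02 - L) × mean score:

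- L = 2%: 0
- L = 5%: -0.03 to -0.09
- L = 10%: -0.08 to -0.24
- L = 20%: -0.18 to -0.54

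**What stays visible.** I used 4,000 simulated trials per scenario, n = 187, 2% post-injection prevalence, and scores 1 to 5 among positives with probabilities 0.45, 0.25, 0.15, 0.10 and 0.05. The table gives the share of trials, among those with at least one positive subject, in which the maximum change exceeds 0.

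| Lifetime prevalence | Past and new independent | New ideation 10 times as likely with history |
|---|---|---|
| 2% | 99.8% | 98.5% |
| 5% | 99.7% | 96.9% |
| 10% | 99.2% | 93.7% |
| 20% | 98.3% | 88.3% |

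For individual subjects: the squared probabilities sum to 0.30, so a positive subject with history has a change of zero or less with probability (1 + 0.30)/2 = 0.65. At 10% lifetime prevalence the share of positive subjects affected is 0.10 × 0.65 = 6.5% under independence. With a risk ratio of 10, the share with history is 1.0/1.9 = 0.53, and 0.53 × 0.65 = 34%.

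**If the Protocol 17.7 t-test is run.** A separate simulation with no drug effect (scores uniform on 1 to 3, 5% lifetime and 1% visit-window prevalence) gives a mean change of -0.084 at n = 187. The two-sided 5% paired test rejects in 62%, 92% and 95% of runs at n = 120, 187 and 200. With matched windows, across all the prevalences tried, the mean is about 0 and rejection is 0 to 4%.

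**The case against.** The strongest reply is that no new event is lost. Post-injection scores come from the Since Last Visit form, so new ideation or behavior gives a non-zero observed score whatever the history. SAP 2.8 lists all records, and SAP 2.9 reports the maximum. New ideation could also be reported as an adverse event, counted by preferred term and session, though no section links a positive C-SSRS to an adverse event. This stands, and it limits the finding to the mean change. It does not make that mean interpretable.

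The SAP's redefinition of intensity refers to the category present at the assessment, which might be read as current. That wording defines how intensity is scored; it does not alter the Day 1 recall window in Protocol 16.9 or touch the ideation and behavior sums.

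The Protocol leaves detailed methods to the SAP, and SAP 2.9.2 makes the change descriptive, so the rejection rates above matter only if the Protocol test is kept. A descriptive mean carries the same shift.

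The size is wholly assumed, and exclusion criterion 10 lets the investigator exclude some psychiatric conditions, which may make the 20% row less plausible. It does not remove past ideation generally.

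The C-SSRS forms and the table shells are not in the supplied text. The Baseline form might also collect a recent window, and a count table might already be planned; neither can be checked.

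**Conclusion.** The concern holds. As written, the Session 1 mean C-SSRS change compares different recall windows, can only be shifted toward apparent improvement, and should not be read as a post-injection effect. The direction follows from the design. The size depends on lifetime prevalence, which the documents do not give: under the assumptions above the mean runs from 0 at 2% lifetime prevalence to between -0.18 and -0.54 at 20%.

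The finding is confined to Session 1. Sessions 2 to 4 use the Since Last Visit form before and after injection. Within Session 1, a positive change in a subject with no lifetime history is a true new onset.

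**What to change.** In SAP 2.9.2 and 5.12:

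- Drop the Session 1 mean change from the lifetime form. If the Baseline form also records a recent period, name that value as the Day 1 baseline and compute the change from it. State which Day 1 value enters the redefined intensity score.
- Remove the reference to inferential statistics from 5.12, and state that this supersedes the paired t-test in Protocol 17.7.
- Report the number and percent of subjects with any post-injection ideation (categories 1 to 5) and any behavior (categories 6 to 10), by maximum category, by session and overall, cross-tabulated against lifetime history. If the unseen shells already hold such a table, cite it in the text and add the lifetime split.
- Keep the listings.

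The cost is SAP text and a few table shells. The data are already collected.

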16.10 Concomitant Medications

In general, concomitant medications that interfere with neuromuscular function or have the potential to confound effectiveness/safety results with regard to sialorrhea will not be allowed during the study, including:

- Aminoglycoside antibiotics (not allowed for entire study);
- Curare-like agents (not allowed for entire study);
- Anticholinergics and Antihistamines
 - Strictly prohibited if used for the treatment of sialorrhea, with the exception of ALS subjects as noted in exclusion criterion #9, which allows for ALS subjects to continue anticholinergic/antihistamine treatment for sialorrhea provided that they continue or convert to a short-acting medication (duration of action approximately 8 hours or less) at a stable dose/regimen for at least 2 weeks before the first injection of study drug (Day 1 of Treatment Session 1). The ALS subject must continue to meet all other eligibility criteria following such conversion/dose stabilization. The ALS subject must hold the medication 8 hours before any clinic visit.
 - Antihistamines and anticholinergic medications taken for a non-sialorrhea condition should be avoided as much as possible, but are not exclusionary.
- Botulinum toxin type A (not allowed for entire study); and
- Botulinum toxin type B, except that provided as study drug.

Additionally, Coumadin (warfarin) and similar anti-coagulant medications will not be allowed during the study.

Other medications not listed above, either specifically or by category, that do not interfere with neuromuscular function or do not have a potential to confound safety/effectiveness results with regard to sialorrhea, may be used by subjects in this study, at the discretion of the Principal Investigator.

17 STATISTICS

Detailed methodology for the summary and statistical analysis of the data collected in this study will be documented in a Statistical Analysis Plan (SAP), which will be prepared and finalized before database lock.

17.1 General Statistical Considerations

Categorical variables will be summarized in general using frequencies and percentages, whereas continuous variables will be summarized in general using descriptive statistics of number of observations (n), mean, standard deviation (SD), minimum (Min), median, and maximum (Max).

